
- 1
- 2
- 3
- 4 51. Martin MM, Rubin RB. A new measure of cognitive flexibility. *Psychol Rep*
- 5 1995;76(2):623-26.
- 6 52. Kamper SJ, Maher CG, Mackay G. Global rating of change scales: a review of strengths
- 7 and weaknesses and considerations for design. *J Man Manip Ther* 2009;17(3):163-70.
- 8 53. Larsen DL, Attkisson CC, Hargreaves WA, et al. Assessment of client/patient
- 9 satisfaction: development of a general scale. *Eval Prog Plann* 1979;2(3):197-207.
- 10 54. Bouwmans C, Krol M, Severens H, et al. The iMTA productivity cost questionnaire: a
- 11 standardized instrument for measuring and valuing health-related productivity losses.
- 12 *Value Health* 2015;18(6):753-58.
- 13 55. World Health Organization. International ethical guidelines for health-related research
- 14 involving humans: Geneva: Council for International Organizations of Medical
- 15 Sciences 2016.
- 16
- 17
- 18
- 19
- 20
- 21
- 22
- 23
- 24
- 25
- 26
- 27
- 28
- 29
- 30
- 31
- 32
- 33
- 34
- 35
- 36
- 37
- 38
- 39
- 40
- 41
- 42
- 43
- 44
- 45
- 46
- 47
- 48
- 49
- 50
- 51
- 52
- 53
- 54
- 55
- 56
- 57
- 58
- 59
- 60

For peer review only

Authors' contributions:

PK and MH wrote the initial draft manuscript. All authors (PK, POS, AS, TH, AC, AM, JH, KOS, AV, JPC, RS, RL, SA and MH), contributed to and revised subsequent drafts and approved the final version.

Funding statement:

This work is supported by National Health and Research Council (www.nhmrc.gov.au) grant number APP1145271, however the Council has no role in study design, data collection, management, analysis, and interpretation of data, writing of reports and the decision to submit any report for publication. The trial team will have unrestricted access to the final trial dataset.

Competing interests statement:

JPC, KOS and POS deliver continuing education workshops on Cognitive Functional Therapy, for which they receive honoraria. The authors declare no other competing interests.

Figure legends:

Figure 1: Flow chart

Figure 2: Placement of the ViMove2 movement sensors

Figure 3: Example movement data (flexion) graphically analysed and displayed by the ViMove2 software

Protocol version:

Version 1, 12 April 2019

Table 1: Trial data collected and their purpose

Construct	Measure	Time points (weeks)	Purpose
Age	Date of birth	0	Describe population
Sex	Male/Female	0	Describe population
Duration of episode	Weeks	0	Describe population
Duration since care-seeking	Weeks	0	Describe population
Previous lifetime episodes	Number	0	Describe population
Height	Centimeters	0	Describe population
Weight	Kilograms	0	Describe population
Education	Categorical	0	Describe population
Current role	Categorical	0	Describe population
Employed	Yes/No	0	Describe population and analysis of economic efficiency
Occupation	Open text	0	Describe population and analysis of economic efficiency
Hours working	Hours	0	Describe population and analysis of economic efficiency
Days working	Days	0	Describe population and analysis of economic efficiency
Sick leave last 3/12	Yes/No	0, 12, 26, 40 and 52	Describe population and analysis of economic efficiency
Days of sick leave 3/12	Days	0, 12, 26, 40 and 52	Describe population and analysis of economic efficiency
Pain-related physical activity limitation	Roland Morris Disability Questionnaire ⁴⁷	0, 3, 6, 12, 26, 40 and 52	Describe population, primary outcome, analysis of economic efficiency

Functional limitation	Patient-Specific Functional Scale ⁴⁸	0, 3, 6, 12, 26, 40 and 52	Secondary outcome
Pain intensity	Numeric Pain Rating Scales ³¹	0, 3, 6, 12, 26, 40 and 52	Describe population, secondary outcome
Fear avoidance beliefs	Fear Avoidance Beliefs Questionnaire (physical activity sub-scale) ³⁵	0, 12, 26, 40 and 52	Describe population, secondary outcome, mediator
Analgaesic use	Participant self-report text box	0	Describe population, secondary outcome (when matched to 12-month Pharmaceutical Benefits Scheme data)
Catastrophising	Pain Catastrophizing Scale ³³	0, 3, 6, 12, 26, 40 and 52	Describe population, secondary outcome, mediator and moderator
Pain self-efficacy	Pain Self-efficacy Questionnaire ³⁴	0, 3, 6, 13, 26, 40 and 52	Describe population, secondary outcome, mediator and moderator
Quality-adjusted life years	EuroQOL EQ-5D-5L ⁴⁹	0, 12, 26, 40 and 52	Analysis of economic efficiency outcome
Treatment expectations	A tailored question, based on Rofail, Myers and Froggatt 2016 ⁵⁰	0 (post-randomisation)	Clinical effectiveness baseline covariate
Confidence in intervention	A tailored question, based on Rofail, Myers and Froggatt 2016 ⁵⁰	3 (CFT groups only)	Mediator
Cognitive flexibility	Cognitive Flexibility Inventory ⁵¹	0	Moderator

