12 biofeedback (n=164). Inclusion criteria include: adults with a current episode of LBP >3
13 months; sought primary care ≥ 6 weeks ago for this episode of LBP; average LBP intensity of
14 ≥ 4 (0-10 scale); at least moderate pain-related interference with work or daily activities. The
15 CFT only and CFT-plus-movement-sensor-biofeedback participants will receive seven
16 treatment sessions over 12 weeks plus a 'booster' session at 26 weeks. All participants will be
17 assessed at baseline, 3, 6, 13, 26, 40 and 52 weeks. The primary outcome is pain-related
18 physical activity limitation (Roland Morris Disability Questionnaire). Linear mixed models
19 will be used to assess the effect of treatment on physical activity limitation across all time
20 points, with the primary comparison being a formal test of adjusted mean differences between
21 groups at 13 weeks. For the economic (cost-utility) analysis, the primary outcome of clinical
22 effect will be quality-adjusted life years measured across the 12-month follow up using the
23 EQ-5D-5L.

1
2
3 1 Ethics and dissemination: Approved by Curtin University Human Research Ethics Committee
4
5 2 (HRE2018-0062, 6th Feb 2018). Study findings will be disseminated through publication in
6
7 3 peer-reviewed journals and conference presentations.
8
9

10 4 Trial Registration: Australian and New Zealand Clinical Trials Register:
11
12 5 ACTRN12618001396213
13
14
15 6
16 7
17
18

19 8 **Strengths and limitations of this study:**

- 20
21 9 • The first fully powered study comparing Cognitive Functional Therapy to usual care as
22
23 10 control
24
25 11 • Three-arm trial to quantify the added contribution of movement sensor biofeedback to
26
27 12 Cognitive Functional Therapy
28
29 13 • Evaluation of whether cognitive or movement changes mediate improvements
30
31 14 • Evaluation of economic efficiency in addition to clinical effectiveness
32
33 15 • Full participant and therapist blinding not possible
34
35
36
37 16
38
39 17
40
41

42 18 **Keywords**

43
44 19 Low back pain, wearable electronic devices, rehabilitation, clinical trial protocol
45
46
47
48
49
50
51
52
53
54
55
56
57
58
59
60

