6 including patient demographics and outcome measures, via the online database. A researcher
7 will be available by phone if they require assistance. A detailed description of the baseline
8 variables is provided in Table 1.

9 10 **Randomisation**

11 After completing the baseline assessment, dynamic (adaptive) random allocation will be used
12 to randomise participants to treatment groups. Randomisation using a 1:1:1 allocation ratio
13 will be conducted by a research assistant by phoning the NHMRC Clinical Trials Centre (24-
14 hour phone service), thereby ensuring concealment of treatment allocation. The NHMRC
15 Clinical Trials Centre will be blinded to baseline assessment. After randomisation and only
16 for those randomised to the CFT-only and CFT-plus-movement-sensor-biofeedback groups, a
17 research assistant will make an appointment for them with a study clinician at an accessible
18 location in their city.

19 20 **Study treatment**

21 *Group 1: Usual care*

22 This treatment will be the usual care pathway the participant's health providers recommend
23 and/or the participant chooses. Treatment in this group will not be impacted in any way by
24 participation in the study. Participants in this group only will be paid a token reimbursement
25 for their time completing follow-up questionnaires (AU\$30 for the 3-month questionnaire,

1 \$30 for the 12-month questionnaire and an additional \$50 if they complete all the six follow-
2 up questionnaires (3 and 6 week, 3, 6, 9 and 12 month).

3 4 *Commonalities across the two CFT treatment groups (Groups 2 and 3)*

5 Both CFT treatment groups will have the same treatment frequency of seven treatment
6 sessions over 12 weeks plus a 'booster' session at 26 weeks (initial consultation 60 minutes,
7 follow ups 30-40 minutes), in physiotherapy clinics. In both groups, clinicians will use a
8 structured approach to address the relevant cognitive, emotional and behavioural (functional
9 and lifestyle) factors deemed relevant to the individual's presentation¹⁷.

10
11 Based on prior screening (Orebro Musculoskeletal Pain Questionnaire and the Patient-
12 Specific Functional Scale) combined with a comprehensive interview and functional
13 examination, the clinician will identify the multidimensional contributors to pain, distress and
14 disability. This will enable the physiotherapist to design a management plan that is tailored to
15 the person's unique clinical presentation and context.

16

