24 the patient nor the clinician will have access to it (only the researchers have access). The
25 ViMove2 device (DorsaVi P/L, Melbourne, Australia) consists of miniaturised sensors

1 attached to the lumbar spine with hypoallergenic tape, and communicate wirelessly with a
2 tablet or mobile phone (Figure 2). At all treatment sessions, patients in both CFT groups will
3 perform forward bending in standing and two other clinically-relevant functional movements
4 selected by the physiotherapist based in the patient specific functional scale. All three
5 movements will be repeated three times and data recorded via the movement sensors.

6 7 *Differences across the two CFT treatment groups*

8 *Group 2: Cognitive Functional Therapy only (CFT-only)*

9 Clinicians and patients in this group will be blinded to all movement sensor output by a
10 software block that only allows the sensors to be configured/started and for the data to be
11 automatically uploaded to a secure cloud-based server. Participants will be told the device is
12 being used to collect outcome data.

13 14 *Group 3: CFT-plus-movement-sensor assessment and biofeedback (CFT-plus-movement- 15 sensor-biofeedback)*

16 Clinicians in this group will treat patients with the same CFT approach as in the CFT-only
17 group except that in addition, these clinicians will have access to data measured by the
18 movement sensors and be able to use these data for assessment, movement retraining and
19 providing biofeedback. The identification of clinically relevant functional movement
20 behaviors in this particular treatment group will also be informed by data from the movement
21 sensors that are graphically analysed and displayed by the ViMove2 software (Figure 3).

22
23 This additional information could assist in guiding individualised movement retraining
24 incorporating the following strategies. Firstly, ‘live assessment’ can assist in identifying
25 unusual kinematic parameters or movement patterns.²⁶ Secondly, ‘live training’ in the clinic,

1 allows visual interaction by observing real-time kinematic and EMG on-screen data to
2 facilitate changing functional movement behaviours. Thirdly, using the ViMove2 software,
3 clinicians can program movement sensor biofeedback alerts (audio ‘beeps’ and messages via
4 a trial-supplied iPhone) that will reinforce key principles from the treatment session while the
5 participant goes about their normal daily activities for the rest of the day. The device will

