- 2 • Pain catastrophisation (Pain Catastrophizing Scale)³³
- 3 • Pain self-efficacy (Pain Self-efficacy Questionnaire)³⁴
- 4 • Fear of movement (physical activity subscale of the Fear Avoidance Beliefs Questionnaire)³⁵
- 6 • Patient-perceived global improvement (1 question)³⁶
- 7 • Patient satisfaction with care and treatment (1 question)³⁷
- 8 • Adverse events (defined as any morbidity or events causing unwarranted distress to a participant that were potentially related to any trial-related intervention). Clinicians and follow-up questionnaires will inquire about any adverse events.
- 11 • Lumbosacral movement will be measured in both CFT treatment groups using ViMove2 wearable wireless sensors and used in the mediation analysis.
- 13 • Direct health costs attributable to consumption of health care resources (measured using extracts from Medicare and Pharmaceutical Benefits databases and direct patient reports) and productivity costs (measured using the iMTA Productivity Cost Questionnaire³⁸).

17 **Sample size calculation**

18 The sample size was calculated for the primary outcome using the program STATA. A total
19 of 492 patients (164 per group) will be recruited to detect a difference of 2 points (0-24 scale)
20 on the RMDQ between the CFT-only group and CFT-plus-movement-sensor-biofeedback
21 group, $p < 0.05$, 80% power, a common standard deviation of 6 points and a worst-case
22 scenario of 20% drop-out rate. Based on our pilot study results^{20 39}, we hypothesise that the
23 CFT-plus-movement-sensor-biofeedback group would have an average score of 7.5 points on
24 the RMDQ and the Usual care group would have a score of 11.5 points. Pragmatically and
25 arbitrarily, we assume the CFT-only group will have a mean outcome that is half-way (9.5)

1 between the other two groups and so we will power the trial to detect this as the smallest
2 likely between-group difference ($11.5-9.5=2.0$).

4 **Blinding**

5 Patients will not be informed of any anticipated results of the trial and will be told that the
6 trial is comparing usual care to two evidence-based interventions. All outcome measures will
7 be either self-reported by patients via web-based questionnaires or collected via the
8 movement sensors or MBS/PBS registers. Unblinded clinicians will deliver only type of one
9 treatment and play no role in collecting data, other than performing a standardised movement

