10 protocol with the resultant movement data being automatically uploaded by the sensors to a
11 server without clinician input. Statisticians will be blind to groups.

13 **Statistical analysis**

14 Almost all participant-reported data will be entered directly into an electronic database,
15 where range values are automatically checked. In addition, all data will be checked for range
16 values and outliers prior to analysis.

18 *Treatment efficacy analysis*

19 Repeated-measure linear mixed models will be used to assess the effect of treatment on pain-
20 related physical activity limitation across all time points (3, 6, 13, 26, 40 and 52 weeks), with
21 the primary comparison being a formal test of adjusted mean differences between groups at
22 13 weeks using intention-to-treat principles. Appropriate sensitivity analyses will be
23 performed on multiple imputed datasets. Estimates of treatment effect will be adjusted for
24 baseline scores of symptom duration, pain intensity, activity limitation (RMDQ score),
25 treatment expectations and significant clinician cluster effects.

1
2
3 1 The secondary outcome measures will be evaluated using the equivalent repeated-measure
4
5 2 linear mixed models.
6
7
8 3

9
10 4 As widely recommended, we will focus on reporting the size of the effect and its uncertainty
11
12 5 (including describing compatibility intervals and p-values) rather than making judgements
13
14 6 based on an arbitrary p-value threshold⁴⁰⁻⁴². In the papers that report the outcomes of this
15
16 7 clinical trial, effect sizes will be discussed relative to those obtained by other interventions in
17
18 8 comparable populations.
19
20
21 9

22 23 24 10 *Analysis of economic efficiency*

25
26 11 Direct healthcare and indirect (productivity) costs incurred by participants will be measured
27
28 12 over the 12-month follow-up period. Direct health costs will be collected using Medicare
29
30 13 Benefits Scheme (MBS) and Pharmaceutical Benefits Scheme (PBS) database extractions,
31
32 14 and patient questionnaires to capture other health care costs (e.g. hospitalisations). Indirect
33
34 15 health costs (e.g. travel to appointments) and productivity costs (including absenteeism and
35
36 16 presenteeism) will also be captured in the 3-monthly patient questionnaires. Productivity
37
38 17 costs will be measured using the 'iMTA Productivity Cost Questionnaire'. Productivity costs
39

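### The primary model adjusts for treatment expectations as a baseline score, but the item is collected after randomisation, so the adjustment can distort the estimated effect of assignment, most clearly for each CFT arm versus usual care

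*Supplement*

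**What the plan says.** All references are to the revised protocol manuscript (R1).

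- **Statistical analysis, Treatment efficacy analysis.** The treatment effect is adjusted for "baseline scores of symptom duration, pain intensity, activity limitation (RMDQ score)", followed by "treatment expectations and significant clinician cluster effects". The resulting adjusted difference at 13 weeks is the primary comparison, under intention-to-treat principles. Secondary outcomes use the equivalent models, so they take over the same covariates.
- **Table 1, Treatment expectations row.** The time point is "0 (post-randomisation)" and the purpose is "Clinical effectiveness baseline covariate". No other row carries this timing note.
- **Randomisation.** For the rest of the baseline data the order is the reverse: "After completing the baseline assessment, dynamic (adaptive) random allocation will be used".
- **Strengths and limitations.** "Full participant and therapist blinding not possible".
- **Blinding.** Patients will be told that the "trial is comparing usual care to two evidence-based interventions. All outcome measures will" be self-reported or collected from sensors or registers.
- **Table 1, next row.** Confidence in the intervention, asked at week 3 in the CFT groups and adapted from the same source as the expectations item, is classed as a mediator.

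**The concern.** A covariate belongs in the primary model of a randomised trial if allocation cannot have affected it. By the plan's own table, this one is recorded once allocation has been made. Someone assigned to usual care gets no study appointment and no new therapy; someone assigned to either CFT arm gets an appointment with a study clinician. Both have been told that the other two options are evidence-based. Answers to a question about expected benefit can then differ by arm because of allocation.

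If they do, two things follow from conditioning on the answer. Any part of the effect that works through expectation is subtracted. And participants are compared across arms at equal post-allocation expectation, a comparison that randomisation does not protect: an unmeasured cause of both expectation and outcome now biases it. The aim of this pragmatic superiority trial is the total effect of being assigned to CFT, and the planned contrast can depart from it. The only sensitivity analyses mentioned use multiply imputed data, which leaves the problem untouched, and no analysis without the covariate is planned.

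**Working it through.** **1. The plan's own figures.** Sample size calculation hypothesises RMDQ means of 11.5 (usual care), 9.5 (CFT only) and 7.5 (CFT plus biofeedback). Hence usual care minus CFT only = 11.5 − 9.5 = 2.0, and usual care minus CFT plus biofeedback = 11.5 − 7.5 = 4.0. Both are used below.

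The 164 per group does not follow from the stated inputs. With difference 2, SD 6, two-sided 5% (sidedness is not stated) and 80% power, 142 evaluable per group are needed, and 142/0.8 gives 178 to recruit. At 164 × 0.8 = 131.2 evaluable, power is 77.0%. An unstated gain from baseline adjustment could explain the gap. Nothing in this point rests on it; 131.2 and 77.0% serve only as the reference below.

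**2. Formula.** Let *a* be the between-arm difference in expectation in SD units, and *b* the within-arm slope of RMDQ improvement on expectation, in points per SD. In a linear model:

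adjusted effect = total effect − *a* × *b*

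The slope *b* includes both a causal effect of expectation and any association due to common causes. If *a* = 0 the shift is zero.

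**3. Inputs.** The documents give neither *a* nor *b*. Assumed: *a* from 0.3 to 1.0 SD, *b* from 0.5 to 1.5 points per SD, higher expectation going with better outcome.

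**4. Results.** Power = Φ(effect/SE − 1.96), with SE = 6 × √(2/131.2) = 0.741 and SD held at 6.

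| *a* | *b* | Shift | True 2.0 becomes (share lost) | Power, from 77.0% | True 4.0 becomes (share lost) | Power, from over 99.9% |
|---|---|---|---|---|---|---|
| 0.3 | 0.5 | 0.15 | 1.85 (7.5%) | 70.4% | 3.85 (3.75%) | 99.9% |
| 0.8 | 1.0 | 0.80 | 1.20 (40%) | 36.7% | 3.20 (20%) | 99.1% |
| 1.0 | 1.5 | 1.50 | 0.50 (75%) | 9.9% | 2.50 (37.5%) | 92.1% |

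**5. Simulation check** (400,000 simulated participants, true difference 2.0).

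- *a* = 0.5, causal *b* = 1.2, no common cause: unadjusted 2.01, adjusted 1.41; the formula gives 2.0 − 0.6 = 1.40.
- *a* = 0.5, no causal effect of expectation, but an unmeasured factor raising expectation and improving outcome: unadjusted 2.01, adjusted 1.61. Confounding alone moves the estimate.
- *a* = 0, with both mechanisms present: unadjusted 1.96, adjusted 1.97. Without an arm difference there is no distortion, which is why a measurement taken before allocation would be safe.

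**The case against.** The documents nowhere say in words that participants have been told their arm when they answer, and the wording of the tailored question is not shown, so it is unknown how far allocation moves the answers. That stands, and it is why the claim is that the estimate can be distorted, not that it is. The timing note and the open comparison with usual care make the inference reasonable all the same.

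Four stronger readings might be inferred; the documents do not support them.

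- **All three contrasts are biased.** The two CFT arms share a treatment schedule and wear sensors for the same duration and frequency. Of the CFT-only group the plan says "Clinicians and patients in this group will be blinded to all movement sensor output by a" software block, and its participants are told that the device collects outcome data. Answers at week 0 may differ little between these arms.
- **The analysis is not intention-to-treat.** Adjustment moves nobody out of the randomised arm. The fault is in what the contrast estimates.
- **The effect must shrink.** That needs expectation both to differ by arm and to go with better outcome. The documents fix no direction for the confounding part. If the shift is attenuation, it is conservative for superiority and costs power rather than producing false positives.
- **Participants unhappy with their allocation will skip the item and drop out of the model.** Nothing in the documents suggests this.

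The percentages also need care. The plan first attaches the 2-point difference to the comparison of the two CFT arms, the least exposed one, and then derives it as 11.5 − 9.5, usual care versus CFT only. For CFT plus biofeedback versus usual care the right yardstick is 4 points, where the same shift is half as large in relative terms.

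**Conclusion.** The point holds. A variable recorded after allocation is labelled a baseline covariate and enters the primary model, and no planned analysis leaves it out. For each CFT arm versus usual care the adjusted contrast can depart from the total effect of assignment; for CFT only versus CFT plus biofeedback the risk is there but probably smaller.

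The size is unknown. The illustrative shift of 0.15 to 1.5 RMDQ points rests wholly on assumed values, on a linear model and on higher expectation accompanying better outcome. Under those assumptions a 2-point effect could lose anything from a small to a major share, while a 4-point effect would still be detected with power above 90%. The case for changing the plan does not depend on these figures: it follows from when the item is measured.

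**What to change.** 1. Remove treatment expectations from the covariates of the primary model and of the equivalent secondary models.
2. Keep symptom duration, pain intensity and RMDQ, which are collected before randomisation.
3. Correct the Purpose column of the Treatment expectations row in Table 1 so that it no longer calls the item a baseline covariate.
4. Use the item only as a candidate mediator, in line with the week-3 confidence item, or in an analysis labelled exploratory or sensitivity.

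Moving the question ahead of randomisation would help future participants only. Recruitment began on 23 October 2018, so it would not supply a pre-allocation value for those already randomised.

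The cost is a line of analysis wording and one table cell. Some explained variance may be lost; the documents do not show how much.
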